1.4 Exploratory Endpoints

- 1) **Prefrontal Cortical Response to Drug Cues.** Change in blood oxygenation level response to visual opioid drug cues in prefrontal cortex from baseline (Day 1) to end of the target drug dose (Day 19 [additionally Day 31 for 5-dose intervention]) using Functional Near Infrared Spectroscopy (fNIRs).
- 2) **Rebound Ambient Drug Craving.** Change in ambient drug craving as measured by 0-100 VAS delivered via smartphone using the EMA on test days and on the first two days and last 2 days of each treatment dose from end of rebound follow up (Day 21 [Day 33 for 5-dose intervention]) to baseline (Day 1) and to end of the target drug dose (Day 19 [Day 31 for 5-dose intervention]).
- 3) **Rebound Blood Pressure.** Change in blood pressure from end of the target drug dose (Day 19 [Day 31 for 5-dose intervention]) to rebound follow up (Day 21 [Day 33 for 5-dose intervention]).
- 4) **Rebound Heart Rate.** Change in heart rate from end of the target drug dose (Day 19 [Day 31 for 5-dose intervention]) to rebound follow up (Day 21 [Day 33 for 5-dose intervention]).
- 5) **Rebound Respiration.** Change in respiratory from end of the target drug dose (Day 19 [Day 31 for 5-dose intervention]) to rebound follow up (Day 21 [Day 33 for 5-dose intervention]).
- 6) **Long-term Glycemic Control.** Change in HbA1c and fructosamine levels from Day 2 to end of the target drug dose (Day 19 [Day 31 for 5-dose intervention]).

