1.2 Primary Study Endpoints

The primary objectives of this pilot study are 1) to determine whether liraglutide can reduce cue-elicited drug craving over 3-5 weeks while participants are in residential treatment for OUD, and 2) to study whether liraglutide can reduce ambient (daily) drug craving over approximately 21-33 days while participants are in residential treatment for OUD.

- 1) Cue-elicited Drug Craving. Change in self-reported cue-elicited drug craving from baseline (Day 1) to the end of the target drug dose (Day 19 [and additionally until Day 31 for 5-dose intervention]) will be measured on a 0-100 point visual analog scale (VAS), where 0= no craving, 100= maximum craving. Assessments are taken prior to, and immediately after, exposure to visual drug cues in the Cue Response Task.
- 2) Ambient Drug Craving. Change in ambient drug craving over time will be measured throughout the study (Days 1-21 [and additionally until Day 33 for 5-dose intervention]) using a 0-100 VAS delivered via smartphone using Ecological Momentary Assessment (EMA) 4 times per day, on each test day (Days 1 and 19 [and additionally Day 31 for the 5-dose intervention]) and on the first two days and last 2 days of each treatment dose.

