8.2 Sample size determination

This is an exploratory study to accumulate pilot data. The primary endpoint of this study is cue-elicited self-reported craving VAS scores. A sample size of N=20 per group will give 80% power to detect an effect size of 0.91 based on a two-sided two-sample t-test with a significance level of alpha=0.05. Accounting for an estimated 20% attrition rate, we plan to randomize a total of 20*2/0.8=50 patients in the study. To preserve statistical power, the sample will not be balanced with regard to MAT and non-MAT participants.

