8.3 Statistical methods

The primary aim is to test whether liraglutide reduces craving in patients recovering from OUD in residential treatment. Analysis of covariance (ANCOVA) will be used to compare liraglutide versus placebo treatment groups controlling for baseline values of craving. Linear mixed effects models for repeated measurements will also be used to evaluate the difference in changes in these primary outcomes between treatment groups. The baseline and post-treatment outcomes are treated as dependent variables in the mixed model. Subjects with missing values can be incorporated in the mixed model analysis when data are missing at random. The moderating effect will be assessed by adding the interaction term between moderator and treatment group in the models.

SAS (version 9.4) and R (version 3.2.5) software will be used for analyses with a significance level of 0.05. Summary statistics including means, medians, ranges, and standard deviations will be computed for each continuous variable and frequencies with percentages for categorical variables. Identified data outliers will be further examined to determine if they are data entry errors, in which case they will be modified when possible; otherwise, values will be kept for final analysis.

Primary outcomes to assess efficacy are: (1) cue-elicited drug craving rated on a 100-pt VAS; and (2) ambient drug craving, derived from EMA of daily craving throughout the study period. Data analyses for cue-elicited craving will consist of a 2×2 ANOVA with medication status (pre- vs post-medication) as a within-group variable and medication type (liraglutide vs placebo) as a between-group variable.

Secondary analyses of self-reported craving measures will evaluate the role of MAT, specifically BUP/NA, in these results.

EMA and Wearable Assessment: Ambient drug craving derived from the EMA will be analyzed as a multilevel model in the regression framework and will test effects of medication status within-person and medication type between-person. Secondary analyses of EMA will examine the effect of time (e.g. study day) to identify differences across condition in the rate of decline in craving across time.

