Data reduction including derivation of summary features for continuously collected data (e.g., sleep data, physiological data) will be performed before formal statistical analysis. Descriptive analysis will be performed to explore distributions of data and identify potential outliers. Assumptions and goodness of fit of statistical models will be assessed. Missing data, including mobile and ambulatory attrition and drop-out will be examined to ensure the validity of statistical models used. Because ambulatory and mobile monitoring will continue during laboratory assessment days, correlation analyses will be used to confirm the agreement between corresponding measures from the two approaches; this will both speed harmonization for follow-up analyses, and provide additional validation of the measures used in the both cases.

The primary endpoints of the EMA assessment will be the rate of reduction of craving across the approximately 21 day study period in the treatment condition compared to the control condition while controlling for the traditional craving triggers of sleep, stress, hunger, affect, and pain and discomfort. Sleep and activity will be measured using a multimodal approach with self-report via the morning EMA survey and wearable actigraphy to measure and account for subjective biases in sleep timing. Craving reduction will be primarily measured using EMA assessment, and will be modeled using linear mixed models in the multilevel modeling (MLM) framework. In MLM, subject-specific random effects are combined with population-level fixed effects to account for variability both within each individual and between individuals in a manner that allows participants with incomplete data to be included in the model. Craving reduction will be modeled as an effect of time in treatment, and differences in rate of craving reduction will be tested as an interaction between treatment state and time. Drs. [name], [name], and [name] each have extensive experience analyzing similar data in the multilevel modeling framework.

For secondary safety outcomes, intensive longitudinal methods such as time-varying effect models will be used to assess for changes in continuously measured outcomes (e.g. blood pressure, heart rate, respiratory rate, body weight) to account for repeated measures. The proportion of participants experiencing AE and SAE will be compared between treatments using chi-square analysis.

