- Loss of consciousness

Blood Pressure and Heart Rate: Frequent blood pressure measurements with the cuff around the arm or finger may be inconvenient and may produce some discomfort and occasional bruising of the upper arm. There is a minimal risk of skin irritation from the EKG patches.

Blood Sampling: There are minor risks and discomforts associated with blood sampling. We will draw blood from the antecubital veins which may cause a brief period of pain and possibly a small bruise at the site. Occasionally, a person feels faint when their blood is drawn. There is a small risk of bleeding after removal of the needle, which can be prevented by tight compression. Rarely, an infection develops which can be treated. Rarely, a clot could form. It is possible that exposure to needles during blood sampling may serve as a trigger for opioid use for some participants.

Pregnancy: This treatment may hurt an unborn child. Subjects will be advised to use approved birth control such as birth control pills, birth control shots, IUD, diaphragm, or condoms while in this study. Subjects will be instructed to inform us if they become pregnant or father a child while in this study. Women able to become pregnant will have a urine test to make sure they are not pregnant before receiving treatment in this study and

at Day 19 [an additional pregnancy test will be given at Day 31 for the 5-dose intervention]. They will be encouraged to use birth control or refrain from intercourse throughout the study. Study drug will be discontinued in case of pregnancy.

Potential risks associated with exposure to drug-related cues: There is a risk of relapse to those in recovery when they are exposed to drug cues in the cue reactivity task. Participants may experience an increase in craving in response to opioid-related images.

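### Ambient-craving prompts and the opioid-cue task share Days 1, 19 and 31 but not the rebound day; any cue carry-over would bias within-arm rebound downward, and the plan neither orders nor separates the prompts

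*Combined protocol and SAP*

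**What the plan says.** Section 1.2 has ambient craving rated by smartphone "4 times per day, on each test day (Days 1 and 19 [and additionally Day 31 for the 5-dose intervention"), as well as on the first and last two days of each dose. The schedule footnotes in Section 7.2 give the EMA days as 1-3, 6-9, 12-15 and 18-21, with 24-27 and 30-33 added for the 5-dose course. The cue task runs on Days 1 and 19, and on Day 31 for 5-dose participants (Section 7.2). Dosing starts before breakfast on Day 2, so Day 1 is the only full pre-drug EMA day.

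The exploratory rebound endpoint in Section 1.4 is the change "from end of rebound follow up (Day 21 [Day 33 for 5-dose intervention]) to baseline (Day 1) and to end of the target drug dose". Both comparators are cue-task days and the rebound day is not.

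On the effect of the task, Section 10.0 says: "Participants may experience an increase in craving in response to opioid-related images". Section 8.3 notes that "ambulatory and mobile monitoring will continue during laboratory assessment days", and says that the EMA model "will test effects of medication status within-person and medication type between-person". Section 7.2.1 mentions the cue task and the start of EMA twice, in opposite sequence, without fixing an order. No section flags or excludes prompts given after the task.

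**The concern.** Ambient craving is meant to describe ordinary daily craving, whereas the cue task is designed to provoke it. If provoked craving lasts until later prompts, the means for Days 1, 19 and 31 mix the two, and those days carry a lot of weight. Day 1 supplies the whole pre-drug side of the within-person medication-status effect. Days 1 and 19 [31] are both reference points for rebound.

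Two readings are at stake. Within an arm, an inflated reference makes craving after withdrawal look lower than it is, and an inflated baseline makes the fall on treatment look larger. Between arms, the trial's own hypothesis is that liraglutide lowers craving. If that includes the response to cues, the Day 19 reference is inflated less on liraglutide than on placebo, and randomisation does not remove that difference.

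**Working it through.** **The plan's own figure.** Section 8.2 states: "A sample size of N=20 per group will give 80% power to detect an effect size of 0.91 based on a two-sided two-sample t-test". The test is at the 5% level, and the total is raised to 50 to allow for one in five participants being lost. By the noncentral t distribution, power at 20 per group and d = 0.91 is 80.1% (required n is 19.96 per group), and 40/0.8 = 50, so the figures reproduce. They concern cue-elicited craving. No power, SD or specific test is given for rebound in ambient craving.

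**Inputs from the documents.** Four prompts per EMA day; 15 EMA days (3-dose) or 23 (5-dose); cue days 1, 19 [31]; first dose on Day 2.

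**Assumptions, not in the documents.** c = VAS points added to each affected prompt (5, 10, 20); k = affected prompts that day (0 to 4); r = share by which liraglutide reduces the Day 19 [31] cue response (0, 0.5, 1).

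**1. Shift in a cue-day mean:** b = c×k/4.

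| c | k=0 | k=1 | k=2 | k=3 | k=4 |
|---|---|---|---|---|---|
| 5 | 0 | 1.25 | 2.5 | 3.75 | 5 |
| 10 | 0 | 2.5 | 5 | 7.5 | 10 |
| 20 | 0 | 5 | 10 | 15 | 20 |

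**2. Rebound within an arm.** Day 21 carries no shift, so Day 21 minus Day 19 and Day 21 minus Day 1 are each biased by −b. At c=10, k=2, a true 5-point rebound from Day 19 would appear as 5 − 5 = 0.

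**3. Pre-drug to on-drug change within an arm.** In the 3-dose schedule one of the 12 on-drug EMA days (2, 3, 6-9, 12-15, 18, 19) is a cue day, so the bias is b/12 − b = −(11/12)b. That is −4.6 points at b=5 and −9.2 at b=10. Counting Days 20 and 21 as post-treatment days gives −(13/14)b, also −4.6 at b=5. In the 5-dose schedule, with 2 cue days among the 22 EMA days after Day 1, it is −(20/22)b, or −4.5 at b=5.

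**4. Rebound between arms (liraglutide minus placebo).** For Day 21 minus Day 19 the bias is −(1−r)b − (−b) = +r×b. With r=0 it is 0. At b=5 it is +2.5 for r=0.5 and +5 for r=1. For Day 21 minus Day 1 it is 0 in expectation, because Day 1 precedes dosing in both randomised arms.

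**5. EMA slope.** This uses least squares over the EMA days as an approximation to the multilevel model.
- 3-dose: mean day 11.2, sum of squares 622.4. The weights are −10.2/622.4 = −0.0164 for Day 1 and 7.8/622.4 = 0.0125 for Day 19.
- Equal carry-over: −0.00386×b per day in both arms. At b=5 this is −0.019 per day, or −0.4 points over Days 1-21. At b=10 it is −0.039 per day, or −0.8.
- Between arms with r=0.5: −0.0125×0.5b. At b=10 this is −0.063 per day, or −1.3 points over 20 days.
- 5-dose, equal carry-over at b=5: −0.0014 per day, under 0.05 points over Days 1-33.

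**6. With Day 18 [30] as the on-drug reference.** Neither that day nor Day 21 [33] has a cue task, so the terms −b and +r×b drop out of the on-drug rebound contrast.

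**The case against.** The strongest reply is that carry-over is not shown. Section 10.0 says only that craving may increase. The VAS in the cue task is taken immediately after exposure and says nothing about prompts hours later, and no section gives the clock time of task or prompts. With k=0 every figure above is zero. This stands, and the sizes are illustrations.

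A second reply is that efficacy rests on between-arm terms, where equal carry-over cancels. Section 8.3 calls the effect of time a secondary EMA analysis in one place, but then names the rate of craving reduction as the primary EMA endpoint, tested by a treatment-by-time interaction. That comparison moves little. The pooled pre/post fall is in any case confounded with time in residential treatment, and rebound is exploratory in a 50-person pilot. All of this stands and limits the importance of the point. It does not remove the +r×b term.

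A third reply is that deleting post-task prompts would thin the only pre-drug day and leave Day 1 resting on prompts from earlier in the day than the all-day means elsewhere. This also stands, and it is a reason to model those prompts rather than drop them.

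A reader might infer that cue carry-over does raise the baseline and so hides the rebound that the trial wants to detect. The documents do not support this. Carry-over is only possible, masking applies only within an arm, and a drug-dampened cue response would exaggerate rebound on liraglutide in the randomised comparison.

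**Conclusion.** The overlap is real and unaddressed: prompts and cue task share Days 1, 19 and 31, the rebound day is cue-free, and nothing orders or separates the prompts. If craving carries over, within-arm rebound is understated by c×k/4. The pre-to-on-drug fall is overstated by about 11/12 of that in the 3-dose schedule. For c of 5 to 20 and k of 0 to 4, the rebound bias runs from 0 to 20 points, with 5 at c=10, k=2. Between arms the bias is zero if carry-over is equal, and r×c×k/4 in the direction of larger rebound on liraglutide if the drug dampens the cue response.

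These results assume a flat addition to each affected prompt and no carry-over into the next day. Confidence is high for the overlap and low for the size of any bias. The point does not threaten the EMA slope comparison or the sample size of 50. It merits correction because the remedy is cheap.

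**What to change.** 1. **Section 1.4.** Use Day 18 [Day 30 for 5-dose] as the on-drug reference for rebound ambient craving, and keep Day 19 [31] as a sensitivity analysis. Sections 7.2.4 and 7.2.8 already schedule EMA on those days, at the same dose and without a cue task.
2. **Section 8.3.** Record the time of the cue task and add a post-cue-task indicator to the multilevel model for prompts on Days 1, 19 and 31. Do not drop those prompts.
3. **Section 7.2.1.** Start Day 1 prompts before the cue task. Phones are handed out before randomisation. Day 1 has no cue-free pre-drug neighbour among the EMA days, so the timing cannot be repaired once a participant has passed it.

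Cost: the on-drug reference falls one day before the last dose, the model gains one term, and the order of Day 1 procedures becomes fixed. No assessment is added beyond noting the task time. A single common indicator would not absorb a cue response that differs by arm; for rebound, the Day 18 [30] reference deals with that.

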2.0 Background

2.1 Scientific Background and Gaps

An estimated 5.6 percent of the global population used illicit drugs in 2016, with 34 million using opioids; worldwide in 2015, 450,000 people died as a result of drug use, with opioids accounting for 76 percent of deaths in those with drug use disorders [1]. In the United States, in 2017, approximately 51.8 million people aged 12 or older used an illicit drug or abused any psychotherapeutic medication. Of those, 11.4 million used an opioid such as heroin or misused prescription pain relievers [2]. According to the Centers for Disease Control and Prevention, between July 2016 and September 2017 there was a 30% increase in the number of emergency room visit for opioid overdose [3]. There were 70,237 drug overdose deaths reported in the United States in 2017, and of these, 67.8%, or 47,600, involved opioids [4], costing the nation an estimated \$51.2 billion annually [5], or \$504.0 billion (2.8% Gross Domestic Product) when including non-fatal impacts [6].

Glucagon-Like Peptide-1 (GLP-1) and Substance Use Disorder. A great deal of attention has focused on the reward pathway and the view that drugs of abuse hijack natural reward substrates [7, 8]. Drugseeking animals and humans, however, are driven by a need state not unlike that of water, food, or salt [9]. GLP-1 is a hormone produced by L cells in the small intestine that reduces intake of food, in part, by increasing insulin release, decreasing glucagon release, and decreasing gastric emptying [10], producing a 'satiety' effect. GLP-1 is also produced by cells in the nucleus of the solitary tract (NST), and these cells project widely throughout the brain including to reward and feeding circuitry [11, 12]. Treatment with GLP-1 receptor (GLP-1R) agonists inhibits ingestion of palatable sweets, water when thirsty, and salt when sodium deficient [11, 13-19]. As such, treatment with this 'satiety' signal, GLP-1, was predicted to reduce drug seeking and taking in humans, as well as rats.

In preclinical studies, treatment with the GLP-1R agonist, Exendin-4 (Ex-4), has been shown to reduce a conditioned place preference for, and the accumbens dopamine response to, nicotine, cocaine, and amphetamine, and reduces cocaine self-administration in rats [15, 16, 20, 21]. Likewise, treatment with Ex-4, in a dose that does not affect responding for sucrose, decreases fixed and progressive ratio responding for cocaine [18] and, when administered centrally, cocaine-induced reinstatement [22]. Finally, the use of a GLP-1R agonist increases insulin secretion, while inhibiting glucagon, only in response to increases in glucose levels [23, 24]. As such, this treatment can potentially be used in patients with OUD without diabetes without the risk of hypoglycemia. Substantial evidence from randomized controlled trials indicate that the use of a GLP-1R agonist can produce significant, sustained weight loss in obese but non-diabetic people without causing any adverse effects on circulating glucose blood pressure, HbA1c or their lipid profile [25-27], suggesting it could be used safely in OUD patients. GLP-1R agonists, then, are promising for the treatment of substance use disorder (SUD) in humans. Further, the intervention can be readily translated for a new indication, as various formulations of GLP-1R agonists are approved for treatment of obesity and Type 2 Diabetes Mellitus (T2DM) in humans [21, 28] and already are in clinical trials for nicotine and alcohol use disorders [29-34].

2.2 Previous Data

GLP-1 and OUD. No studies to date have tested whether a GLP-1R agonist can reduce responding for opioids in humans. We have shown that administration of Ex-4 (2.4 μg/kg ip) during abstinence and prior to test (i) in rats with a history of heroin self-administration decreased cue-induced heroin-seeking (Figure 1, left) and (ii) abolished drug-induced reinstatement of heroin-seeking (Figure 1, right). In a second preliminary study, we tested the longer acting GLP-1R agonist, liraglutide [0.1 mg/kg subcutaneous, (sc)]. The half-life for liraglutide in rats is about 4 h [35]. Our results showed that daily liraglutide treatment beginning on the 11th day of heroin self-administration and continuing

[figure not shown]

Figure 1: Mean (+/- SEM) number of infusion attempts/h during cued extinction testing (**Left**) and heroin-induced reinstatement testing (**Right**) in rats with a history saline or heroin self-administration and pretreated sc with saline (Veh) or 2.4 ug/kg Exendin-4 (Ex-4).

through abstinence: (i) reduced heroin self-administration (Figure 2, left), (ii) failed to reduce seeking during extinction (Figure 2, middle), possibly due to a slower onset of the longer acting liraglutide (liraglutide was injected 1 h before extinction testing), and (iii) significantly reduced heroin-induced reinstatement of heroin seeking behavior (liraglutide was administered 6 h prior to the reinstatement

test, Figure 2, right). Taken together, these data provide strong support that GLP-1R agonists hold promise as a novel intervention for OUD.

GLP-1R agonist treatment in humans. GLP-1R agonists have been studied for decades and are, as mentioned, an approved and effective treatment for obesity and (T2DM) in humans [27, 36, 37]. In 131 patients with T2DM, treatment with GLP-1R agonists led to significant improvement in glycated hemoglobin (HbA1c) and BMI [38]. Likewise, GLP-1R agonists in patients with T2DM led to controlled

[figure not shown]

Figure 2: Mean (+/- SEM) number of infusions/6h in rats self-administering saline or 0.06 mg/inf heroin iv and treated with saline or liraglutide (0.1 mg/kg sc) (**Left**). Mean (+/- SEM) number of infusion attempts/h during cue-induced extinction (**Middle**) and heroin-induced reinstatement testing in rats with a history saline or heroin self-administration and pretreated with saline or liraglutide (1.0 mg/kg sc) (**Right**).

blood glucose, along with positive effects on body weight, blood pressure, and cholesterol [10]. Furthermore, neuroimaging studies have shown that GLP-1R agonists reduce brain responses to food cues in obese and T2DM participants, but not in lean participants. Specifically, Van Bloemendaal et al. [39] demonstrated that the GLP-1R agonist exenatide (relative to placebo) decreased functional magnetic resonance imaging (fMRI) measures of brain activation in the amygdala, insula, putamen, and, importantly, orbitofrontal cortex (OFC) in response to a series of food related cues (i.e., food vs nonfood pictures) in subjects with obesity and T2DM. This effect was not observed in lean control subjects. The most common side effects of GLP-1R treatment are nausea and diarrhea; less common is injection-site bruising or "reactions" (i.e. erythema, pruritus, and rash) [36]. One meta-analysis found evidence of a slight increase in heart rate, a modest reduction in blood pressure, and no association with hypertension across 60 trials employing 14 different GLP-1R formulations [40]. Further work reported decreased cardiovascular risk [41] and a reduction in major adverse cardiac events including nonfatal stroke, nonfatal myocardial infarction, and cardiovascular mortality [42] in T2DM patients treated with GLP-1R agonists compared with placebo.

All GLP-1R agonists are not the same with regard to treatment of obesity or T2DM. Ex-4 (exenatide) is a short acting GLP-1R agonist with a half-life of 2.4 h in humans [43]. Liraglutide has a longer half-life of about 13 h in humans [44] and, as such, has been found useful as a once/day sc injectable formulation for the treatment of obesity [27, 45] and T2DM [46, 47]. A meta-analysis determined no cause for concern regarding neuropsychiatric safety associated with liraglutide [48].

Although liraglutide was approved for human use in 2010, there are no data testing the effectiveness in patients with an OUD. The objective of the proposed research is to test whether treatment with a GLP-1R agonist can reduce craving in humans with OUD. Here, we will conduct a pilot study to determine whether once daily treatment with liraglutide can safely and effectively reduce craving in patients in a residential treatment facility for OUD, and who are either receiving counseling (CO) or counseling plus a common medication assisted treatment (MAT), buprenorphine/ naloxone (BUP/NA). We chose liraglutide for this initial pilot study as dosing can be closely monitored due to its 13 h half-life and can be safely ramped up to an effective dose during a 4-6 week residential treatment program.

This is an innovative project that will, for the first time, test the safety and efficacy of GLP-1R agonist treatment on opioid craving. Further, because single timepoint self-report measures of craving have not been found to be strong predictors of relapse behavior [49], we will assess craving using an array of verbal, emotional, physiological, and neural indices. Emotional and physiological feedback will be

obtained using both EMA and a wearable device (i.e., a wristband). This will allow us to track not only changes in mood and craving across the day, but also changes in craving that may be elicited by the subcutaneous injection of the GLP-1R agonist or vehicle.

